No relevant hyperglycaemia has been observed so far. Xentuzumab was well tolerated, with no relevant side effects reported. The type and pattern of adverse events (AEs) observed to date have generally been of mild to moderate intensity (CTCAE Grades 1 or 2) or consistent with the safety profile of combination backbone treatment or consistent with the underlying neoplastic conditions of patients enrolled on the study. The most frequently reported AEs for xentuzumab monotherapy were fatigue, decreased appetite, nausea, diarrhoea, and vomiting. Infusion-related reaction (IRR) is a listed side effect of xentuzumab treatment.

Promising early efficacy signals in the dose escalation part of the 2 phase I studies have been observed with two confirmed antitumour responses (Partial Responses) according to RECIST criteria in a patient with nasopharyngeal cancer and a patient with a peripheral primitive neuroectodermal tumour (PPNET) or Ewing sarcoma. Moreover, twelve confirmed disease stabilizations (SD) have been observed in heavily pre-treated patients suffering from advanced or metastatic solid tumours. In the expansion cohorts at R2PD, no further objective responses have been observed.

At a planned interim analysis of the randomized phase II part, based on the recommendation of data monitoring committee, recruitment of phase II part was stopped and xentuzumab treatment was discontinued. According to latest analysis, in the overall population, PFS did not improve with the addition of xentuzumab to everolimus plus exemestane. Nevertheless, a favorable signal was observed in the pre-specified subgroup of patients without visceral metastasis (report [c22665932-01](#)).

In the aforementioned ongoing trial in HR+ metastatic breast cancer, the safety profile of xentuzumab in combination with everolimus and exemestane is considered favourable and as expected, since the observed safety profile of this triple combination is consistent with previously reported data for the combination doublet everolimus and exemestane (Bolero-2 trial) (Baselga et al. 2011: [R12-5635](#)). The same applies for the combination with enzalutamide in CRPC, where the safety profile of this doublet is consistent with previously reported data for enzalutamide (Affirm and Prevail trials) ([R13-1229](#), [R15-1307](#)).

Abemaciclib

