4.1.1 Identity of the Investigational Medicinal Products

Table 4.1.1: 1 Xentuzumab (Investigational product, IMP)

Substance:	Xentuzumab humanized monoclonal antibody
Pharmaceutical formulation:	Concentrate for solution for infusion
Source:	Boehringer Ingelheim Pharma GmbH & Co. KG
Unit strength:	10 mg/ml of xentuzumab supplied in 20 ml vials (200 mg/vial)
Posology	Once weekly administrated through one hour intravenous infusion. Infusion duration may be extended to over one hour and up to a maximum of three hours in cases of grade ≥ 2 infusion reactions
Route of administration:	Intravenous infusion. Appropriate dose of xentuzumab will be diluted in isotonic sodium chloride solution (0.9%)
Duration of use:	Continuous weekly dosing (days 1, 8, 15 and 22 in a 28-day course) in the absence of disease progression, intolerable AEs or other reason necessitating withdrawal

Detailed preparation and handling of xentuzumab, including information on infusion equipment and infusion procedure, will be described in ISF.

Table 4.1.1: 2 Abemaciclib (Investigational product, IMP)

Substance:	Abemaciclib. Small molecule CDK4 and CDK6 inhibitor
Pharmaceutical formulation:	Capsules
Source:	[REDACTED]
Unit strength:	A white hypromellose capsule containing 50 mg of abemaciclib and the inactive ingredients pregelatinized starch, dimethicone, and colloidal silicon dioxide.
Posology	Treatment/28-day cycle 150 mg p.o. Q12H on Days 1-28 (Starting dose Cohort A) Abbreviations: PO = orally; Q12H = every 12 (\pm 2) hours
Route of administration:	p.o.
Pharmaceutical formulation:	Tablets
Source:	[REDACTED]
Unit strength:	Film-coated 50 mg tablets
Posology	Treatment/28-day cycle 150 mg p.o. Q12H on Days 1-28 (Starting dose Cohort A) Abbreviations: PO = orally; Q12H = every 12 (\pm 2) hours
Route of administration:	p.o.

Table 4.1.1: 3 Fulvestrant. Background endocrine therapy. (Auxiliary Medicinal Product, AMP)

Substance:	Fulvestrant (Faslodex®)
Pharmaceutical formulation:	Solution for injection
Source:	[REDACTED]
Unit strength:	Prefilled syringes (250 mg fulvestrant in 5mL solution).
Route of administration:	Intramuscular injection

Table 4.1.1: 3 (cont.) Fulvestrant. Background endocrine therapy. (Auxiliary Medicinal Product, AMP):

Substance:	Fulvestrant (Faslodex®)

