4.1.4.1 Initial study drug assignment and administration

General information that applies in this study regardless of IRT is described in below sections of individual study drug. The medication kit as well as the treatment will be assigned with the support from IRT.

Before entering patients at the next dose level of the dose finding cohorts, it will be ensured that all patients at the current ongoing dose level have completed at least one course of treatment.

Xentuzumab

Patients will start treatment with their assigned dose tier (see [Section 4.1.2](#)) or RP2D of xentuzumab from course 1 day 1. Xentuzumab will be administered at the investigator site intravenously over one hour with a constant infusion rate on the treatment day as specified in the [Flow Chart](#). If scheduled infusion of xentuzumab is not performed within the time window, this treatment will be skipped and will not be made up. Subsequent visits should follow the original visit date schedule. Mannitol is used in the formulation of xentuzumab, so infusion duration of less than one hour must be avoided. The infusion time may be extended to over one hour and up to a maximum of three hours in cases of CTCAE grade ≥ 2 infusion reactions. In case of a delay or an interruption of infusion, the reason and the exact time of deviation must be recorded in the specific eCRF. The accuracy of this information is crucial for the proper evaluation and appraisal of the pharmacokinetics – in the relevant cohorts – and other data.

Detailed information of dispensation, preparation, and handling of xentuzumab will be described in ISF.

Abemaciclib

Abemaciclib will be taken orally every 12 (± 2) hours on days 1 through 28 of a 28-day cycle for a total of 56 doses per cycle. During all cycles, abemaciclib should be taken at approximately the same times each day. If a patient misses or vomits a dose, that dose should be omitted.

No more than 56 doses of abemaciclib should be dispensed for each 28-day cycle.

Abemaciclib dose omissions will be evaluated on a case by case basis and patients may be replaced if dose omissions occur within MTD period of a dose finding cohort or if the number of dose omissions makes the patient non evaluable regardless of the cohort.

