4.4.2 Management and grading of infusion reactions

The xentuzumab infusion should always be administered under close supervision of a medically qualified staff member with immediate availability of appropriate resuscitation facilities.

Infusion reactions may occur during infusion with xentuzumab and include pyrexia, chills, rigors, dyspnoea, urticaria, bronchospasm, hypotension and hypertension. **A one hour observation period is recommended following each infusion.** If there is no infusion reaction during the first treatment course, the observation period following xentuzumab infusion may be adjusted at the discretion of the investigators. Mild to moderate infusion reactions may be managed with a slower infusion rate and prophylactic antihistamines for subsequent dosing. Severe reactions require immediate and permanent discontinuation of infusion. The hypersensitivity reactions will be graded according to the National Cancer Institute (NCI) Common Terminology Criteria for Adverse Events (CTCAE) version 4.03 ([R10-4848](#)).

The infusion duration may be extended to over one hour and up to a maximum of three hours.

The infusion reactions should be treated symptomatically as judged clinically relevant by the investigator. For symptomatic treatment of infusion reactions: hydrocortisone, antihistamines such as chlorphenamine accompanied by an antipyretic/analgesic and/or a bronchodilator is recommended.

Infusion reactions will not be reported on the standard AE page but will be reported on a separate page specifically for infusion reactions in the CRF.

Table 4.4.2: 1 Infusion reaction management

Infusion Reaction Grade	Management
CTCAE Grade 1 or 2	In the event of a CTCAE grade 1 infusion reaction, the infusion rate should be reduced by 50%. A Grade 2 infusion reaction may require symptomatic treatment, as described above (with infusion interruption). Once the event has resolved, the infusion may be restarted at the reduced rate.
CTCAE Grade 3	For patients experiencing a CTCAE grade 3 infusion reaction, infusion should be interrupted immediately and patients should receive aggressive symptomatic treatment, as described above. Only after all the symptoms have disappeared, the infusion may be re-started if it is within 3 hours since the infusion start. The infusion rate should be reduced by half after re-start

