CTCAE Grade 4	Patients experiencing CTCAE grade 4 such as anaphylaxis during an infusion should have infusion immediately stopped and receive appropriate treatment, as described above, including use of resuscitation medications If needed. Such patients should NOT receive any further xentuzumab treatment.

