4.4.3 Management of Neutropenia

Adverse events of neutropenia have been observed in studies with xentuzumab and causality has been established with abemaciclib. Patients should be monitored closely for signs of infection. Dose adjustment for severe neutropenia (\geq Grade 3) should follow as per [Table 4.1.4.2: 1](#) (xentuzumab) and [Table 4.1.4.2: 2](#) (abemaciclib) in the protocol. Fever or infection in the presence of severe neutropenia should be managed promptly with broad-spectrum antibacterial therapy.

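### Section 4.4.2 leaves severe infusion reactions ungraded; on the protocol's own usage its text bars the half-rate restart that Table 4.4.2:1 permits after a Grade 3 reaction

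*Protocol*

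**What the plan says.** The running text of Protocol Section 4.4.2 has two tiers and grades neither. For the lower tier: "Mild to moderate infusion reactions may be managed with a slower infusion rate and prophylactic antihistamines for subsequent dosing". For the upper: "Severe reactions require immediate and permanent discontinuation of infusion". The section names CTCAE version 4.03 as the grading scale but does not map the two tiers to it.

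Table 4.4.2:1, in the same section, works by grade:

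- **Grade 1 or 2:** reduced rate, or interruption and restart.
- **Grade 3:** interrupt at once and treat. Then, "Only after all the symptoms have disappeared, the infusion may be re-started if it is within 3 hours since the infusion start", at half the rate.
- **Grade 4:** stop at once. "Such patients should NOT receive any further xentuzumab treatment". This is the only row with a permanent bar.

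Section 2.3 adds that infusion reactions in this trial are graded and treated by usual standards of care or local guidance. No rule says which instruction takes precedence.

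**The concern.** This is a bedside rule for a listed side effect of xentuzumab, applied under time pressure. If severe includes Grade 3, the text forbids a step that the table allows. After the same Grade 3 reaction, one site could restart at half rate and be following the table. Another could stop for good and be following the text. The word permanent adds a second uncertainty, because it is unclear whether it refers to that day's infusion or to all later ones.

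The question is still live in the current version. The sponsor recommended in October 2021 that xentuzumab be stopped, but Section 3.3.4.2 leaves continuation to the investigator's individual assessment, with the drug's expiry in May 2023 as the outer limit.

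**Working it through.** No figure is involved, so the check is a comparison of passages.

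**Step 1: how the protocol uses the two words elsewhere.**

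- Section 1.2 says that adverse events seen with xentuzumab have "generally been of mild to moderate intensity (CTCAE Grades 1 or 2", and Section 2.3 makes the same equation. If Grades 1 and 2 are mild to moderate, the next tier starts at Grade 3.
- Section 4.4.3, the next subsection, opens its rule with "Dose adjustment for severe neutropenia" and defines that in brackets as Grade 3 or higher.
- Section 4.4.6 says to discontinue abemaciclib for severe ILD/pneumonitis and refers to Table 4.1.4.2:2, where discontinuation is mandatory at Grades 3 and 4. Severe there again covers Grade 3.

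**Step 2: apply each reading of severe to a Grade 3 infusion reaction.**

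| Reading of severe | Text of 4.4.2 | Table 4.4.2:1, Grade 3 | Agree? |
|---|---|---|---|
| Grade 3 or higher | Permanent stop | Restart allowed at half rate | No |
| Grade 4 only | Silent on Grade 3 | Restart allowed at half rate | Yes, but Grade 3 falls in neither tier of the text |

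**Step 3: does the narrow meaning of discontinuation remove the conflict?** Suppose it means only that day's infusion. The table allows that same infusion to be restarted, so under the first reading the conflict remains.

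**Step 4: do other passages settle it?** Several fit the table better:

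- Table 4.1.1:1 says "Infusion duration may be extended to over one hour and up to a maximum of three hours in cases of grade" 2 or higher, and Section 4.1.4.1 says "The infusion time may be extended to over one hour and up to a maximum of three hours in cases of CTCAE grade" 2 or higher. Neither sets an upper grade limit.
- Section 3.3.5 lets patients with hypersensitivity of Grade 3 or higher in cycle 1 be replaced, and replaced patients may continue treatment.

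These passages make the table's rule the more likely intention, but none of them defines severe. The Section 2.3 reference to local guidance does not define it either.

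**Step 5: later weekly doses.** No sentence deals specifically with the next infusion after a Grade 3 reaction. The general rules for interruption (4.1.4.2) and skipped infusions (4.3), together with a permanent bar at Grade 4 only, suggest that later doses are allowed. The word permanent in the text points the other way if severe includes Grade 3.

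**The case against.** The strongest reply is that the conflict is inferred. The meaning of severe is borrowed from neutropenia, from ILD/pneumonitis and from a general summary of past adverse events; none of these defines severity for infusion reactions. Section 4.4.2 supplies a table that covers Grades 1 to 4, and a sensible reader would follow the more specific source and take severe as Grade 4. This has force. It makes the table the likelier intention and limits how firmly the point can be put. It does not remove the ambiguity, because the protocol neither states that reading nor says that the table prevails.

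A second reply is that the Grade 3 row is permissive. A site that ends that day's infusion after a Grade 3 reaction complies with both text and table. That also stands. What remains open is whether the optional restart is allowed and whether later weekly infusions may follow.

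A reader might infer an outright contradiction in the protocol. The documents do not support that, because severe carries no grade and one reading reconciles the two rules. A reader might also infer damage to dose finding, but Section 5.3.7 excepts infusion-related reactions from its general item on non-hematologic toxicity of Grade 3 or higher, and nothing here shows that the MTD or any endpoint would change.

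**Conclusion.** The point holds as a minor inconsistency. Section 4.4.2 does not grade severe. On the protocol's own usage, its text bars the Grade 3 restart that its table permits, and the two agree only on a reading that is never stated. The conclusion rests on one assumption: that severe means for infusion reactions what it means elsewhere in the protocol.

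The consequence is confined to patient safety and uniform conduct across sites. The event is rare: Section 2.3 reports three serious infusion reactions, one of them Grade 3 or higher. These counts do not give a usable rate for this trial, since non-serious Grade 3 reactions are not reported and the number of patients still receiving xentuzumab is not given. No effect on endpoints, MTD or sample size is claimed.

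**What to change.** Make text and table give one rule by grade. The clinical choice is the sponsor's:

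- **(a) If the table is intended:** replace the sentence with wording such as *After a Grade 4 reaction, xentuzumab is stopped at once and not given again; Grade 3 reactions are managed as in Table 4.4.2:1.*
- **(b) If the stricter rule is intended:** write Grade 3 or 4 in the sentence and delete the restart option from the Grade 3 row.

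In the same edit, state in the Grade 3 row whether later weekly infusions are allowed. If they are, specify a reduced rate with premedication, which is how Section 4.4.2 already handles reactions at subsequent dosing. Do not refer to the scheme in Section 4.1.4.2, because that would bring in dose reduction, which Section 4.4.2 does not use for infusion reactions.

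The cost is one sentence and one table row, with no extra data. It does need a small protocol amendment with the ethics and authority review required by Section 8.1, and a notice to sites still giving xentuzumab.

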4.4.3 Management of Neutropenia

Adverse events of neutropenia have been observed in studies with xentuzumab and causality has been established with abemaciclib. Patients should be monitored closely for signs of infection. Dose adjustment for severe neutropenia (\geq Grade 3) should follow as per [Table 4.1.4.2: 1](#) (xentuzumab) and [Table 4.1.4.2: 2](#) (abemaciclib) in the protocol. Fever or infection in the presence of severe neutropenia should be managed promptly with broad-spectrum antibacterial therapy.

4.4.4 Management of Hepatotoxicity

Grade ≥ 3 increased ALT was reported in patients receiving abemaciclib in breast cancer studies. Monitor ALT, prior to the start of abemaciclib therapy, every 2 weeks for the first 2 months, monthly for the next 2 months, and as clinically indicated. Please refer to [Flow Chart](#) for time points. Based on the level of ALT elevations, abemaciclib may require dose modification. (see [Table 4.1.4.2:2](#)).

In addition, for hepatic toxicity, additional monitoring should be considered. Details for hepatic monitoring depend upon the severity and persistence of observed laboratory test abnormalities. If the abnormality persists or worsens, clinical and laboratory monitoring should be initiated by the investigator, based on the hepatic monitoring tests (see [Section 10.5](#)) and in consultation with the Sponsor. Monitoring of ALT, AST, and total bilirubin should continue until levels normalize or return to approximate baseline levels. Additional diagnostic testing should be considered to rule out cause of increased liver enzymes per the investigator's discretion.

4.4.5 Venous Thromboembolism

Venous thromboembolic events were reported in patients receiving abemaciclib plus fulvestrant or aromatase inhibitors in breast cancer studies. The majority of the events were non-serious and were treated with low-molecular-weight heparin. Generally, these events did not result in discontinuation of the study treatment. At this time, the mechanism underlying the association between abemaciclib and the occurrence of VTEs is not known. Monitor patients for signs and symptoms of deep vein thrombosis and pulmonary embolism and treat as medically appropriate.

4.4.6 Guidance for Interstitial lung disease/Pneumonitis

ILD/pneumonitis has been identified as an adverse drug reaction for abemaciclib. Additional information is available in the IB of abemaciclib.

Ask your patients to report any new or worsening respiratory symptoms such as cough, dyspnea, fever, and investigate and treat as per your local clinical practice (including corticosteroids as appropriate). If ILD/pneumonitis is suspected, investigations may include imaging such as high resolution computed tomography (HRCT), bronchoalveolar lavage, and biopsy as clinically indicated. Refer to [Table 4.1.4.2:2](#) for guidance on dose adjustments of abemaciclib for patients with ILD/pneumonitis. Discontinue abemaciclib in cases of severe ILD/pneumonitis.

5. VARIABLES AND THEIR ASSESSMENT

5.1 TRIAL ENDPOINTS

5.1.1 Primary Endpoint(s)

For dose finding cohorts A, B, C, and D (dose finding):

The primary endpoints for each dose finding cohort are the MTD and the number of patients with dose limiting toxicities (DLT) in the MTD evaluation period.

The MTD evaluation period is defined as the first treatment cycle (28 days). The MTD is defined as the highest dose with less than 25% risk of the true DLT rate being above 33%. For definition of DLTs, refer to [Section 5.3.7](#)

A Bayesian Logistic Regression Model (BLRM) employing the escalation with overdose control (EWOC) principle will be used during each dose finding cohort for a selection of doses to investigate and for estimation of the MTD. Cohorts of patients will receive xentuzumab and abemaciclib (with or without endocrine therapy) until the MTD is reached or until the Steering Committee (SC) decides on stopping the dose finding. Each dose-level cohort will consist of newly enrolled patients. Estimation of the MTD during each dose finding cohort of the study will be based upon the estimation of the probability of a DLT in the MTD evaluation period in the set of evaluable patients for MTD. The corresponding methodology is described in [Section 7](#).

The MTD estimate established during the dose finding cohort will be re-investigated after the corresponding expansion cohort by re-running the BLM including all data from dose finding cohort and expansion cohort, in particular also considering the DLT information from all treatment cycles.

For expansion cohort E

The primary endpoint for expansion part is objective response (OR) defined as best overall response of complete response (CR) or partial response (PR), where best overall response is determined according to Response Evaluation Criteria In Solid Tumours (RECIST) version 1.1 from date of first treatment administration (including run-in for cohort E) until the earliest of disease progression, death or last evaluable tumour assessment before start of subsequent anti-cancer therapy.

For expansion cohorts D1 and D2:

The primary endpoint for expansion part is PFS rate at 18 month defined as the rate of absence of disease progression or death at 18th month, where progression is determined according to Response Evaluation Criteria In Solid Tumours (RECIST) version 1.1.

For expansion cohort F

The primary endpoint for expansion part is disease control (DC) defined as best overall response of complete response (CR) or partial response (PR) or confirmed stable disease (SD) (lasting for at least 24 weeks) or Non-CR/ Non-PD (lasting for at least 24 weeks) where best

overall response is defined according to RECIST version 1.1 from first treatment administration until the earliest of disease progression, death or last evaluable tumour assessment before start of subsequent anti-cancer therapy.

5.1.2 Secondary Endpoint(s)

[figure not shown]
For dose finding cohorts A, B, C, and D (dose finding)

[figure not shown]
There are no secondary endpoints.

[figure not shown]
For expansion cohorts E, F, D1 and D2:

The secondary endpoints are:

- * Cohorts D1, D2 and E only: Disease control (DC) defined as best overall response of complete response (CR) or partial response (PR) or confirmed stable disease (SD) (lasting for at least 24 weeks) where best overall response is defined according to RECIST version 1.1 from first treatment administration until the earliest of disease progression, death or last evaluable tumour assessment before start of subsequent anti-cancer therapy.
- * Time to objective response defined as the time from first treatment administration until first documented complete response (CR) or partial response (PR).
- * Duration of objective response defined as the time from first documented complete response (CR) or partial response (PR) until the earliest of disease progression or death among patients with objective response.
- * Duration of disease control defined as the time from first treatment administration until the earliest of disease progression or death, among patients with disease control.
- * Progression-free survival (PFS) defined as the time from first treatment administration until tumour progression according to RECIST 1.1 or death from any cause, whichever occurs earlier.
- * Cohorts D1, D2 and F only: Objective response (OR) defined as best overall response of complete response (CR) or partial response (PR), where best overall response is determined according to Response Evaluation Criteria In Solid Tumours (RECIST) version 1.1 from date of first treatment administration until the earliest of disease progression, death or last evaluable tumour assessment before start of subsequent anti-cancer therapy.

